- iii. A trained and supervised doctoral level therapist will deliver the intervention. Discord or disagreements between children and parents will be addressed in therapy, and one full session of the treatment is devoted toward improving communication skills.
- iv. All data will be coded by number, not name, and a "key" form will be kept in a separate locked file cabinet. No information will be provided about the patients enrolled in this study to anyone outside of the clinical and research teams, except in emergency situations (e.g., patient deemed a threat to him/herself or others) or as required by law (e.g., child abuse/neglect). The study therapists are all doctoral level with substantial experience handling crises. If a therapist learns of potential abuse/neglect, they will notify the Connecticut Department of Children and Families (DCF) as required by law. If a therapist has concerns about potential suicidal or homicidal ideation, the therapist will conduct a comprehensive risk assessment and, if deemed necessary, the participant will be transported immediately to the emergency room for acute evaluation and treatment. Within the research context, research assistants may also hear indications of risk of harm to self or others or abuse/neglect. RAs will be well-trained on how to handle these situations. Specifically, the RA will immediately contact the PI, study coordinator, or study therapist who will assess safety and manage the crisis directly or instruct the RA on how to address risk, including (if necessary) arranging for transportation to an emergency room or reporting concerns about abuse or neglect to DCF.

Audio data will be collected digitally, will be stored on a password protected secure server, and destroyed at the end of the study; only research personnel will review the audio files for training, supervision, and adherence monitoring purposes. As noted earlier, an audiotaping section within the consent form will be used in the study, and patients may participate in the study without allowing audiotaping. All audio files will be labeled by number, not name, and the "key" form will be kept separate in a locked file cabinet.

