- v. It is possible that the increased monitoring of Internet activity that is part of the behavioral treatment may lead to uncovering illegal Internet activity on the part of the youth. During the informed consent procedure, youth and parents will be informed of this risk. It will also be made clear to the parents and youth that any information disclosed to the research team that indicates that the patient is a threat to him/herself or others will be reported as required by law to the Connecticut Department of Children and

Families (DCF). See 2biv above for details. It is possible that other behaviors (e.g., buying/selling) that are illegal but do not require mandated reporting may be uncovered by increased parental monitoring. Although these situations do not represent a threat to confidentiality, they may lead to loss of the patient's privacy and could cause increased conflict in the parent-child relationship. This risk is similar to that in adolescent substance abuse treatment, when parents are encouraged to increase monitoring through random urine drug screens and room searches. This risk will be mitigated by 1) as noted above, informing both parent and youth about this potential risk as part of the informed consent procedure; 2) closely following mandated reporting laws in handling this information; 3) teaching skills in treatment (e.g., communication) that can help parents and youth negotiate conflict situations; and 4) provision of individualized referrals to help address any conflict or symptoms that persist. Of note, these risks are similar to those that would occur in outpatient family-based treatment in the community, which commonly focuses on increased parental monitoring and supervision of children's behaviors.

c. Potential Benefits of the Proposed Research to the Subjects and Others.

The anticipated benefits to participants in the study include careful evaluation of the child's game playing, substance use and psychosocial and family functioning, and a potential for reducing their game playing. Parents and children will each receive \$30 in gift cards for the intake and 4 week follow-up and \$50 for the post-treatment and 4-month follow-ups. Total compensation is up to \$160 per family member.

Benefits to society include a potential improvement in the effectiveness of treatment for Internet gaming disorder.

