(C) A trained and supervised doctoral level therapist will deliver the intervention. Discord or disagreements between children and parents will be addressed in therapy, and one full session of the treatment is devoted to improving communication skills.

(D) All data will be coded by number, not name, and a "key" form will be kept in a separate locked file cabinet. No information will be provided about the patients enrolled in this study to anyone outside of the clinical and research teams, except in emergency situations (e.g., patient deemed a threat to him/herself or others) or as required by law (e.g., child abuse/neglect). The study therapists are all doctoral level with substantial experience handling crises. If a therapist learns of potential abuse/neglect, they will notify the Connecticut Department of Children and Families (DCF) as required by law. If a therapist has concerns about potential suicidal or homicidal ideation, the therapist will conduct a comprehensive risk assessment and, if deemed necessary, the participant will be transported immediately to the emergency room for acute evaluation and treatment. Within the research context, research assistants may also hear indications of risk of harm to self or others or abuse/neglect. RAs will be well-trained on how to handle these situations. Specifically, the RA will immediately contact the PI, study coordinator, or study therapist who will assess safety and manage the crisis directly or instruct the RA on how to address risk, including (if necessary) arranging for transportation to an emergency room or reporting concerns about abuse or neglect to DCF.

All audiorecordings will be stored digitally on a password protected secure server and destroyed at the end of the study; only research personnel will review the recordings for training, supervision, and adherence monitoring purposes. An audiorecording section within the consent form will be used in the study, and patients may participate in the study without allowing audiorecording. All audio files will be labeled by number, not name, and the "key" form will be kept separate in a locked file cabinet.

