(E) It is possible that the increased monitoring of Internet activity that is part of the behavioral treatment may lead to uncovering illegal Internet activity on the part of the youth. During the informed consent procedure, youth and parents will be informed of this risk. It will also be made clear to the parents and youth that any information disclosed to the research team that indicates that the patient is a threat to him/herself or others will be reported as required by law to the Connecticut Department of Children and Families (DCF). See 17D above for details. It is possible that other behaviors (e.g., buying/selling drugs, gambling) that are illegal but do not require mandated reporting may be uncovered by increased parental monitoring. Although these situations do not represent a threat to confidentiality, they may lead to loss of the patient's privacy and could cause increased conflict in the parent-child relationship. This risk is similar to that in adolescent substance abuse treatment, when parents are encouraged to increase monitoring through random urine drug screens and room searches. This risk will be mitigated by 1) as noted above, informing both parent and youth about this potential risk as part of the informed consent procedure; 2) closely following mandated reporting laws in handling this information; 3) teaching skills in treatment (e.g., communication) that can help parents and youth negotiate conflict situations; and 4) provision of individualized referrals to help address any conflict or symptoms that persist. Of note, these risks are similar to those that would occur in outpatient family-based treatment in the community, which commonly focuses on increased parental monitoring and supervision of children's behaviors.

**18. Collection and reporting of SAEs.** See Section 12.

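### Families are to be told that a threat to self or others is reported to the state child-protection agency (DCF), but the procedure cited for details contains no such step

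*Combined protocol and SAP*

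**What the plan says.** Two sections prescribe what families hear during informed consent about the limits of confidentiality.

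- **Detailed Data and Safety Monitoring Plan, 17(E).** The message begins "It will also be made clear to the parents and youth that any information disclosed to the research team" and goes on to say that disclosures suggesting a participant "is a threat to him/herself or others will be reported as required by law to the Connecticut Department of Children and Families (DCF"). It then adds "See 17D above for details".
- **Human Subjects, 2.b.v.** The same sentence appears, with the words "is a threat to him/herself or others will be reported as required by law to the Connecticut Department of Children and" leading to the rest of the agency's name. It points to 2.b.iv for details.

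The two cited sections, 17(D) and 2.b.iv, share nearly identical text on staff procedure.

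- Confidentiality may be broken "in emergency situations (e.g., patient deemed a threat to him/herself or others) or as required by law (e.g., child abuse/neglect").
- For abuse or neglect: "If a therapist learns of potential abuse/neglect, they will notify the Connecticut Department of Children and Families (DCF) as required by law".
- For ideation: "If a therapist has concerns about potential suicidal or homicidal ideation, the therapist will conduct a comprehensive risk assessment". Transport to the emergency room follows only where it is judged necessary.
- Research assistants who hear of either contact the PI, study coordinator or study therapist at once. The possible actions listed are emergency-room transport and a report of abuse or neglect concerns to DCF.

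**The concern.** A statement about the limits of confidentiality tells participants what will happen to what they say. Here it describes a report that the procedure offered as its explanation does not include. It also leaves out the one situation in which that procedure does send a report to the agency.

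The situation is foreseeable in this trial. The protocol's abstract, specific aims and background link gaming problems to suicidality. Section 12 of the monitoring plan lists onset of clinically significant suicidal ideation and of homicidal ideation among its SAE types. Sections 17(D) and 2.b.iv expect that both therapists and research assistants may hear indications of harm.

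Two things are at stake: whether families consent or assent on an accurate account, and whether staff who follow the written procedure also keep the undertaking given at consent.

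There is an age gap as well. Enrolment covers ages 10-19, and adult children sign their own consent. None of the four sections says whether the route through a children's agency applies to participants aged 18-19.

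**Working it through.** No figure is involved, so there is nothing to recompute. The check sets the four sections side by side.

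| Situation | Statement to families: 17(E), 2.b.v | Staff procedure cited: 17(D), 2.b.iv |
|---|---|---|
| Threat to self or others | Reported to DCF, with a legal-requirement qualifier | Example of an emergency exception to confidentiality; recipient not named |
| Suicidal or homicidal ideation | Not named separately | Risk assessment, then emergency room where judged necessary; DCF not mentioned |
| Abuse or neglect | Not mentioned in the statement | Example of a legally required disclosure; therapist notifies DCF |
| Research assistant hears of risk or abuse | Not addressed | Immediate contact with PI, coordinator or therapist; emergency room for risk, DCF for abuse or neglect |
| Participant aged 18-19 | Not addressed | Not addressed |

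1. **Where DCF appears in the procedure.** Section 17(D) names the agency twice, once in the therapist route and once in the research assistant route. Both mentions concern abuse or neglect. Section 2.b.iv is the same.
2. **Where the legal requirement attaches.** In the procedure, the example of a legally required disclosure is abuse or neglect, and a threat is the example of the other category, an emergency. The statement to families attaches the legal requirement and DCF to the threat.
3. **Whether the cross-reference resolves the difference.** It does not. A reader sent to 17(D) or 2.b.iv for details of a DCF report after a threat finds none there.
4. **Whether the two can be followed together.** They can. Nothing in 17(D) or 2.b.iv forbids a DCF report after a threat, and one participant could have a risk assessment, an emergency transfer and a report. But a staff member working only from the procedure would have no instruction to make that report.

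So the statement names a report that the procedure does not describe, and omits the one that it does.

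**The case against.** The strongest reply is that the sentence is loose rather than wrong. Its legal-requirement qualifier can be read as a condition, meaning a report only where the law calls for one. The rest of 17(E) fits that reading: it sets apart illegal behaviours outside mandated reporting and promises to follow the reporting laws closely. The triggers also differ. The statement concerns information showing that the patient is a threat, while the procedure starts from concern about possible ideation, so a youth who mentions suicidal thoughts falls first under the risk assessment. Finally, staff do have a stepwise procedure, and the consent forms may already separate the two routes.

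Much of this stands. The conditional reading is available, and the forms cannot be checked. It does not remove the mismatch. Even read conditionally, the statement links DCF to threats, while the procedure identifies only abuse or neglect as a reason to notify the agency. The statement still omits that reason.

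Stronger readings are tempting, but the documents do not support them.

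- A reader might infer that staff cannot obey both sections. They can, as step 4 of the comparison shows.
- A reader might infer that the procedure reserves DCF for abuse or neglect. It names the agency only there, but it does not exclude other use.
- A reader might infer that the warning will suppress disclosure of ideation, lower SAE counts or distort symptom self-reports. The documents give no rate or evidence for this. Emergency disclosure and possible emergency-room transport already apply, so any added deterrent from naming DCF is unknown.
- A reader might infer that suicidal ideation is the event on which the safety plan relies most. Section 12 lists three SAE types without ranking them, and the stopping rule in section 15 singles out none.

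**Conclusion.** The point holds as an inconsistency between the planned statement to families and the staff procedure it cites. It occurs twice, in 17(E) against 17(D) and in 2.b.v against 2.b.iv.

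Its reach is the consent discussion for all 60 planned families, because consent and assent come before randomization. It has no numerical size, and no effect on safety counts or outcome data is claimed.

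The conclusion assumes that the consent discussion follows the protocol as written. If the forms already separate the two situations, the protocol text still needs correcting, but participants would not have been misinformed by the forms. The documents cannot settle which reporting route is right, and no view is taken on that here. Because it concerns what participants are told about confidentiality, it should be corrected.

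**What to change.** Reconcile 17(E) with 17(D), and 2.b.v with 2.b.iv, so that the statement to families and the staff procedure give the same trigger and the same route for (a) a threat to self or others and (b) abuse or neglect. Say explicitly whether either route differs for participants aged 18-19. Then check that the consent and assent forms, and the instructions to the research staff who obtain consent, carry the reconciled version. The choice of route belongs to the investigator and the IRB.

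The cost is a few sentences in two places, any matching change to the forms, and a minor IRB amendment. No data collection or analysis changes.
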